8.3	Scientific Advisory Board.....	51
8.4	DATA SAFETY MONITORING BOARD (DSMB)	52
9.0	TRIAL MANAGEMENT.....	52
9.1	Statistical Management.....	52
9.2	Data Management.....	52
9.3	STUDY MONITORING.....	53
9.4	PROJECT MANAGEMENT.....	54
10.0	GUIDE TO ACRONYMS / DEFINITIONS	55
11.0	Classes of Anti-Arrhythmic Drugs (Vaughn-Williams Classification)¹²⁷.....	56
12.0	LITERATURE CITED	57

PROTOCOL SYNOPSIS

Title	Vein of Marshall Ethanol Infusion for Persistent Atrial Fibrillation
IND Sponsor	Houston Methodist Research Institute (HMRI) [name]
Name of Product	Dehydrated Alcohol Injection, USP
Clinical Phase	III
Patient Population	Patients with documented, persistent atrial fibrillation (AF that persists beyond 7 days) that have failed to respond to at least one class of antiarrhythmic drugs (due to failure or intolerance), and who are otherwise deemed candidates for radiofrequency ablation of AF.
Objectives	VENUS-AF. Vein of Marshall Ethanol iNfusion in Untreated perSistent Atrial Fibrillation: To assess the role of VOM ethanol infusion in catheter ablation of persistent AF. MARS-AF. Vein of Marshall Alcohol in Repeat ablation of perSistent Atrial Fibrillation: To assess the impact of VOM ethanol infusion after a failed conventional ablation of persistent AF.
Trial Design	Subjects who meet inclusion criteria will be randomized to either a conventional PVAI or PVAI with VOM procedure. Subjects will return for follow-up evaluations at 1, 3, 6, 9, and 12 months. One-month continuous cardiac event monitoring will be performed at 6 months and at 12 months. Studies performed at follow-up visits may include EKG, physical exam, QOL questionnaires, echocardiography, laboratory studies, anticoagulation therapy, and management of adverse events and AF recurrences. Patient and co-investigator performing follow-up of electrocardiographic data will be blinded to the type of procedure. Operator is not blinded.
Sample Size	405 total subjects, VENUS: 180 (VOM-PV) + 156 (PVAI) = 336 MARS: 37 (VOM-PV) + 32 (PVAI) = 69
Primary Endpoints	Efficacy: Freedom from symptomatic AF or atrial tachycardia (AT) AND reduction of AF/AT to less than 30 seconds in a continuous monitor at 6 and 12 months after a single procedure. Safety: Acute procedural complications and total mortality De Novo (VENUS-AF) and Previously Failed Ablation (MARS-AF)

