5.5 STUDY PROCEDURES

SCREENING/BASELINE

1. Initial assessment.

After signing informed consent, the following data will be collected; a significant medical history and recent targeted physical exam, electrocardiogram (EKG), echocardiogram within one year prior to the procedure for evaluation of cardiac structure, and function, and laboratory tests. In addition, a review of medications that patient is taking (limited to AAD and anticoagulants), and a quality of life (QOL) questionnaire especially developed for AF (AFEQT)¹¹³ will be filled out by patients.

Screening assessments performed pre-consent signature that are completed under standard of care can be included as viable source documents for patient study inclusion/exclusion and may be collected to screen potential study patients.

2. Pre-procedural imaging.

Imaging prior to enrollment is required to rule out structural heart disease and, as needed, to rule out the presence of LA appendage thrombus. *Ruling out LAA thrombus can be performed by the following: TEE, CT or MRI within 48 hours of the*

procedure; at least one month of oral anticoagulation prior to the procedure; or documented prior procedures of LAA occlusion or ligation. For ruling out structural heart disease, either a cardiac MRI, CT or transthoracic echocardiogram within 1 year prior to participation in the study is sufficient. Documentation by exception (ie. no LAA thrombus documented on imaging report) is permitted for determination of eligibility. Left atrial diameter and estimated left atrial volume will be obtained from any of these diagnostic modalities. There is no specific requirement for a pre-ablation CT or MR, since anatomical details of the LA can be obtained intra-procedurally with current mapping systems.

3 Randomization.

Randomization should take place after confirmation that all inclusion/exclusion criteria are met and measurements of LA volume are obtained. Patients will be randomized in a 1.15:1 fashion (to account for an 85% technical feasibility of the VOM procedure) to receive either VOM-PV or the conventional PVAI. Patients will be blinded to the randomization outcome.

PROCEDURE/DAY 0:

1 PVAI procedure

As part of a conventional catheter ablation of AF the following will be performed, all considered standard of care:

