6.0 STATISTICAL CONSIDERATIONS

A) Assumptions.

Single-procedure versus multiple-procedure success. Our initial preliminary data suggested an overall procedure success of 45% in patients undergoing PVAI and 61% for those undergoing VOM-PV (difference of 16%). This included patients with repeat procedures performed in some, but not all of the failed procedures (45% all patients in the PVAI group and 30% in the VOM-PV group). **The single-procedure success was 38% in patients undergoing PVAI and 56% in patients undergoing VOM-PV** (difference of 18%). Thus, the endpoint of single-procedure success is likely to show greater differences amongst groups.

Mortality. The expected mortality is low in this study as it has been in AF ablation trials.

Mortality will be recorded as a safety endpoint.

One-year follow-up time. In previous versions of the protocol, additional follow-up time (up to 15 months) was included in the VENUS trial, in order to accommodate for appropriate follow-up of patients undergoing repeat procedures. Therefore, a trial duration of 12 months is sufficient if just single-procedure success is the primary efficacy endpoint. Procedural failures (events counted as the primary efficacy endpoint) occur mostly during the first year. Additionally, 12-month follow-up is consistent with the recommendations for clinical trials in AF by the HRS/EHRA/ECAS Catheter and Surgical Ablation consensus document.²

Unknown classification as success or failure. Patients who cannot be classified as successes or failures on the primary efficacy endpoint will be excluded from the primary analysis.

B) VENUS Group Sequential Clinical Trial Design

Power and sample size determination. Group sequential two proportions power analysis using simulation was performed using PASS V12 (Kaysville, UT). The following assumptions were made:

- Response rate in PV-VOM: $p_1=0.56$
- Response rate in PVAI: $p_2= 0.38$
- Hypotheses: $H_0: p_1= p_2$; $H_1: p_1 \neq p_2$
- Test Statistic: Z-Test (Unpooled)
- Zero Adjustment Method: None
- Alpha-Spending Function: O'Brien-Fleming Analog
- Beta-Spending Function: None
- Futility Boundary Type: None
- Number of Looks: 3
- Simulations: 100000

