Results. A group sequential trial with sample sizes of N1=180 and N2=156 at the final look achieves 91% power to detect a difference of 0.18 between a treatment group success proportion of 0.56 and a control group success proportion of 0.38 at the 0.05 significance level (alpha) using a two-sided Z-Test (Unpooled). The table below lists the sample sizes required for 91% power.

Table 5. Sample size requirements for a group sequential trial based on 100,000 iterations.

Value	95% LCL	95% UCL	Target	Actual	95% LCL	95% UCL	Beta		
0.909	0.908	0.911	0.050	0.049	0.048	0.051	0.091		
----- Average Sample Size -----									
-- Given H0 -- -- Given H1 --									
N1	N2	Grp1	Grp2	Grp1	Grp2	Diff0	Diff1	P1 H1	P2
180	156	179	155	144	125	0.00	0.18	0.56	0.38

Efficacy Monitoring. We propose to monitor efficacy at two interim time points and one final time period (i.e., three “looks”) when primary outcome data (12 month follow-up) are available for 1/3, 2/3 and 3/3 of the total sample size of VENUS subjects. For the VENUS trial, these values are provide in the following table in terms of *information time*:

Table 6. Efficacy monitoring schedule for VENUS with cumulative sample size, significance boundaries and 95%CIs, and alpha- and beta-spending.

Accumulated primary outcomes for VENUS						
Look	Accumulated Sample Size -----					
	Percent	VOM	PVAI	Total		
1	33.33	60	52	112		
2	66.67	120	104	224		
3	100.00	180	156	336		

Significance Boundaries with 95% Simulation Confidence Intervals						
Look	----- Z-Value Boundary -----			----- P-Value Boundary -----		
	Value	95% LCL	95% UCL	Value	95% LCL	95% UCL
1	+/- 3.953	3.809	4.289	0.000	0.000	0.000
2	+/- 2.543	2.516	2.578	0.011	0.010	0.012
3	+/- 2.011	1.994	2.036	0.044	0.042	0.046

Alpha-Spending						
Look	----- Target -----			----- Actual -----		
	--- Signif. Boundary---	Spending	Spending	Proportion	Cum.	
Z-Value	P-Value	Function	Function		H1 Sims	H1 Sims
Look	Scale	Scale	Alpha	Alpha	Cum. Alpha	Outside Signif. Boundary
1	+/- 3.953	0.000	0.000	0.000	0.000	0.033
2	+/- 2.543	0.011	0.012	0.011	0.012	0.547
3	+/- 2.011	0.044	0.038	0.038	0.049	0.329
						0.909
		Spent	Spent	Boundary		Cum. Boundary

The hypothesis test applied at the k th look is a two-tailed test of equality of two independent proportions, functionally composed as

$$Z_k = \frac{\hat{p}_{1k} - \hat{p}_{2k}}{\sqrt{\frac{\hat{p}_{1k}(1-\hat{p}_{1k})}{n_{1k}} + \frac{\hat{p}_{2k}(1-\hat{p}_{2k})}{n_{2k}}}}$$

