where \hat{p}_{1k} is the proportion of successful primary outcomes in the PVAI-VOM arm of VENUS at the k th look, and \hat{p}_{2k} is the proportion of successful primary outcomes within the PVAI arm of VENUS at the k th look. Z_k follows a standard normal distribution, $N(0,1)$. If during the first look when at least $N=60$ VOM and $N=52$ PVAI primary outcomes have been observed ($N=112$ total), if Z_1 exceeds 3.953, then the trial will be evaluated for early termination due to beneficial efficacy, whereas if the power is 30% or less, the trial will be evaluated for early termination for futility. However, if the power of the test falls in the “promising zone” (30-70%), we will continue the trial. The same rule applies for the 2nd look when at least $N=120$ VOM and 104 PVAI primary outcomes (224 total) have been observed in both arms, for which the tabled critical value of Z_2 is ± 2.543 . The overall efficacy of the trial will be determined when at least $N=180$ VOM and $N=156$ (336 total) primary outcomes have been observed, for which the critical value of Z_3 is ± 2.011 .

[figure not shown]

Figure S1. Efficacy boundaries at 33%, 66%, and 100% accrual of VENUS primary outcomes.

VENUS Interim Analysis - Conditional Power and Futility For Various Test Results.

During the interim analysis, estimations of conditional power and futility will be performed, to provide information for clinical trial continuation decisions. The sample size will not be subject to any changes.

Conditional power runs were made using PASS 12 (Kaysville, UT). During the first look at 33% information time, there will be 60 VOM and 52 PVAI primary outcomes available. Using a one-sided ($\alpha=0.025$) test of two proportions, $\theta=p_2-p_1$, where p_2 is the PVAI success rate and p_1 is the VOM success rate, the expectation is that the test statistic Z_k is less than zero, since $H_a: p_2 < p_1$. The table below list the conditional power and futility at the first look for a range of Z_k values:

Table 7. VENUS Conditional power and futility at the first look (33% information, 60 VOM, 52 PVAI) for a range of Z_k values from a one-sided test of two independent proportions.

Cond. Power	Pred. Power	Total Sample Size VOM/PVAI	Current Sample Size n1k n2k	Prop. Group 1 P1	Prop. Group 2 P2	Test Statistic Z _k	Alpha	Futility
0.99994	1	180 156	60 52	0.56	0.38	-5	0.025	0.00006
0.99974	0.99998	180 156	60 52	0.56	0.38	-4.5	0.025	0.00026

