Missing data. The critical piece of data required for endpoint analysis is the electrocardiographic event monitor. Failure to comply with wearing the monitor will lead to missing data. We request patients to wear monitors for 1–month. However, only a minimum of 1-week of monitored time is required for Endpoint assessment. Patients with less than 1 –week of monitoring will be considered as missing data. Patients who die before then study end will be considered not to have a response to treatment. For patients with missing primary outcomes, we will perform multiple imputation (MI) based on Monte Carlo Markov chain (MCMC) methods (Refs 1-3). MI will only be used for dealing with missing data as a secondary analysis tool of the primary endpoint. In Stata, MI is available for many procedures, especially the regression modules (linear, logistic, Poisson, Cox PH). MI can be performed to iteratively impute central estimates of missing outcome measures based on subjects' covariate patterns. The most straightforward example can be envisioned in this study, where logistic regression with MI is employed to train a model based on primary outcome (0-failure,1-success) as the dependent variable and age, gender, baseline AF duration, and baseline LA volume as independent predictors to impute $P(y=1|x)$ for subjects with missing primary outcome.

Sensitivity analysis. Following methods introduced in Proschan et al. (Ref 4), we simulated success rates for patients with missing 12-month outcomes in VOM and PVAI arms for VENUS and MARS at 33%, 66%, and 100% information time (looks 1-3). $B=100,000$ iterations were used with proportions of $P_m=0, 0.05, 0.10, 0.15$, and 0.2 representing the amount of missing data in both VOM and PVAI arms. At look k , let the success rate in the VOM arm be p_{1k} and the success rate in the PVAI arm be p_{2k} , n_{1k} and n_{2k} the number of patients accrued in the VOM and PVAI arms, $n_{1k}^m = n_{1k}P_m$ and $n_{2k}^m = n_{2k}P_m$ the number of patients in VOM and PVAI arms with missing outcome data, and $n_{1k}^0 = n_{1k} - n_{1k}^m$ and $n_{2k}^0 = n_{2k} - n_{2k}^m$ the number of patients in VOM and PVAI arms without missing outcomes. Next, for VOM patients with missing

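### The 91% VENUS power assumes that all 336 randomised patients are analysed, although unclassifiable patients are excluded, and the final-look trigger cannot be met after a single exclusion

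*Combined protocol and SAP*

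**What the plan says.** - **Size and power.** The Synopsis gives "VENUS: 180 (VOM-PV) + 156 (PVAI) = 336". Section 6.0 B uses the same two arm sizes at the final look and says the design "achieves 91% power to detect a difference of 0.18 between a treatment group success proportion of 0.56" and a control proportion of 0.38 (Table 5: 0.909).
- **Exclusion rule.** Section 6.0 A: "Patients who cannot be classified as successes or failures on the primary efficacy endpoint will be excluded from the primary analysis". Under Missing data, less than one week of monitoring counts as missing, and "MI will only be used for dealing with missing data as a secondary analysis tool of the primary endpoint".
- **Timing of looks.** Looks occur "when primary outcome data (12 month follow-up) are available for 1/3, 2/3 and 3/3 of the total sample size of VENUS subjects". For the last one: "The overall efficacy of the trial will be determined when at least" 180 VOM and 156 PVAI outcomes, 336 in total, have been observed, with critical value 2.011.
- **No re-sizing.** The VENUS interim-analysis paragraph adds: "The sample size will not be subject to any changes".
- **Allocation.** Section 5.5: "Patients will be randomized in a 1.15:1 fashion (to account for an 85% technical feasibility of the VOM procedure").
- **MARS.** The Synopsis plans 37 + 32 = 69. Section 6.0 C powers and monitors it at 33 + 33 = 66, with a printed power of 0.810.

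**The concern.** The number randomised equals the number in the power calculation, so nothing is set aside for patients whom the plan itself removes. Three features look like an allowance: the unequal allocation, multiple imputation and the missing-data tables. None of them supports the 91% for the primary analysis. A neutral VENUS result would then be read against a power somewhat higher than the design delivers.

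The exclusion rule and the final-look trigger also conflict. With 336 enrolled and no provision for replacement, the first unclassifiable patient makes 336 observed outcomes impossible. Read literally, the final analysis then has neither a date nor a critical value laid down in advance. That choice should not be left until data are in hand.

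**Working it through.** **Inputs.** Rates 0.56 and 0.38, unpooled two-sided Z, three looks at 60/52, 120/104 and 180/156, boundaries 3.953, 2.543 and 2.011 (section 6.0 B, Table 6). The documents give no exclusion rate. The 0 to 20% grid of the Sensitivity analysis tables is used as an assumed range, with equal shares lost from both arms at every look.

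**1. Reproduce the plan's figure.** Simulating the three-look design with the printed boundaries gives 0.910 (printed 0.909). A closed-form check at the final look agrees:

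SE = √(0.56·0.44/180 + 0.38·0.62/156) = 0.05366; 0.18/0.05366 = 3.355; Φ(3.355 − 2.011) = 0.910.

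**2. Apply the exclusion rule.** Same rates and boundaries, fewer patients:

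| Excluded | Final VOM/PVAI | Closed form | Simulated, three looks |
|---|---|---|---|
| 0% | 180/156 | 0.910 | 0.910 |
| 5% | 171/148 | 0.896 | 0.895 |
| 10% | 162/140 | 0.879 | 0.88 |
| 15% | 153/133 | 0.861 | 0.86 |
| 20% | 144/125 | 0.839 | 0.84 |

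**3. Does 1.15:1 hold anything back?** All 180 VOM patients are already counted in the 91%. An equal split of the same total, 168/168, gives 0.907 simulated (0.911 in closed form). The ratio is worth nothing material either way. It equalises the number treated (0.85 × 180 = 153 against 156) and adds no reserve.

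**4. Do the missing-data tables give power?** No. The formula in the Sensitivity analysis holds the observed success rates fixed and randomises only the imputed outcomes, with 1.96 as the cut-off. At 100% information and 0% missing, 0.56 vs 0.38 prints 1.000, where the design has 0.909. For 0.56 vs 0.43 it prints 1.000, where single-look power is Φ(0.13/0.0542 − 1.96) = 0.67.

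**5. Can the trigger be met?** Enrolled 336, required 336, so any exclusion defeats it. At an assumed 1% exclusion rate, the chance of at least one among 336 is 1 − 0.99^336 = 0.966.

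**6. What follows for alpha?** Keeping the printed VENUS boundaries with 5 to 20% lost gives a simulated two-sided alpha of about 0.050 to 0.051. Re-deriving them by simulation from the O'Brien-Fleming-type spending function moves the final value only from 2.013 at 336 outcomes to 2.001 at 319, 1.993 at 302 and 1.982 at 269. Power is unchanged to the accuracy shown above.

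**7. MARS.** With the printed boundaries (5.014, 2.708, 2.055) and rates 0.76 and 0.42, simulated power is about 0.825 at 33/33 (printed 0.810) and about 0.816 at the planned 37/32. A PVAI look size of 33 cannot be reached with 32 randomised. MARS figures jump by a point or two because the counts are small.

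**The case against.** **The 91% is not wrong.** This stands. The calculation reproduces, its inputs are listed as assumptions, and every power figure is conditional on its inputs. A reader might infer an arithmetic error; there is none.

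**Exclusions should be few.** This largely stands. One week of monitoring is enough, and death, clinical recurrence and repeat ablation all count as failures (sections 5.7 and 5.8), so those patients remain classifiable. Even 20% leaves power at 0.84.

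**The sample-size sentence is about interim re-estimation.** This stands too. It sits in the paragraph on conditional power, so it should not be read as forbidding replacement of unevaluable patients. But nothing in the plan provides for replacement, so the conflict between trigger and exclusion rule remains.

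**The trigger hardly matters.** The statistic uses the actual arm sizes and a final critical value is printed. Step 6 confirms that alpha is safe either way. What is missing is a written rule.

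**A tempting stronger reading is that failed cannulation cuts the real power to about 0.80.** The documents do not support this. It needs the pilot 0.56 to exclude failed cannulations and undelivered patients to respond at the PVAI rate; neither is stated. Under both assumptions the VOM rate is 0.85 × 0.56 + 0.15 × 0.38 = 0.533 and VENUS power is about 0.80 (about 0.84 at 90% delivery). For MARS the rate is 0.709 and power about 0.67. If the pilot rates already include failed cannulations, there is no dilution. Nor can one assume that only cannulated patients will be analysed: section 6.0 B counts the whole 180-patient arm, and the cross-over paragraphs of 5.7 and 5.8 compute endpoints by original randomised group.

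**Conclusion.** The point holds as one about a stated power and a decision rule. The 91% is right for complete outcomes at 0.56 vs 0.38. Under the plan's own exclusion rule it is about 0.895 at 5%, 0.88 at 10% and 0.84 at 20%. These exclusion rates are assumed and the low end is the more plausible. The final-look counts are incompatible with that rule as soon as one patient is unclassifiable. A reader might infer that type I error control fails or that the final test becomes invalid; the simulations show neither for VENUS. The MARS mismatch between 33/33 and 37/32 is real; it costs about one point on a like-for-like simulation and leaves power no lower than the printed 0.810. Severity: minor. Confidence is high on the VENUS arithmetic and on the textual conflict. The dilution question remains open because the documents do not say which patients the pilot rates describe.

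**What to change.** Sample size, test and alpha stay unchanged.

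1. In section 6.0 B, state that 91% assumes a classifiable outcome for all 336 patients, and add power over 0 to 20% exclusions (step 2). Do not present the Sensitivity analysis tables as power.
2. Replace the minimum counts with a rule such as: *Interim looks use the primary outcomes available. The final look takes place when all randomised patients have completed or left follow-up.* State in advance whether it uses the printed VENUS boundaries or boundaries re-derived, by the same kind of simulation as Table 6, from the stated spending function. If they are re-derived, use simulation: normal-theory boundaries with this unpooled Z give a two-sided alpha of about 0.052 for VENUS and 0.065 for MARS at 37/32.
3. Re-run the MARS power and boundaries at 37/32. A simulated re-derivation gave 5.416, 2.770 and 2.052, with power 0.814.
4. As a secondary clarification, say whether the pilot 0.56 and 0.76 include failed cannulations.

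The cost is SAP wording and one re-run of the power program. The stated power becomes slightly less favourable, no patients are added, and the final VENUS critical value hardly moves.

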0.9991	0.99978	180 156	60 52	0.56	0.38	-4	0.025	0.0009
0.99717	0.99814	180 156	60 52	0.56	0.38	-3.5	0.025	0.00283
0.99209	0.98894	180 156	60 52	0.56	0.38	-3	0.025	0.00791
0.98027	0.95313	180 156	60 52	0.56	0.38	-2.5	0.025	0.01973
0.95597	0.85624	180 156	60 52	0.56	0.38	-2	0.025	0.04403
0.91184	0.67408	180 156	60 52	0.56	0.38	-1.5	0.025	0.08816
0.84101	0.43598	180 156	60 52	0.56	0.38	-1	0.025	0.15899
0.74056	0.2196	180 156	60 52	0.56	0.38	-0.5	0.025	0.25944
0.61467	0.08289	180 156	60 52	0.56	0.38	0	0.025	0.38533

Table 8. VENUS Conditional power and futility at the second look (66% information, 120 VOM, 104 PVAI) for a range of Z_k values from a one-sided test of two independent proportions.

Cond. Power	Pred. Power	Total Sample Size VOM/PVAI	Current Sample Size n1k n2k	Prop. Group 1 P1	Prop. Group 2 P2	Test Statistic Z _k	Alpha	Futility
1.00000	1.00000	180 156	120 104	0.56	0.38	-5.0	0.025	0
1.00000	1.00000	180 156	120 104	0.56	0.38	-4.5	0.025	0
0.99998	0.99998	180 156	120 104	0.56	0.38	-4.0	0.025	0.00002
0.99973	0.99950	180 156	120 104	0.56	0.38	-3.5	0.025	0.00027
0.99703	0.99233	180 156	120 104	0.56	0.38	-3.0	0.025	0.00297
0.97954	0.94042	180 156	120 104	0.56	0.38	-2.5	0.025	0.02046
0.90942	0.75562	180 156	120 104	0.56	0.38	-2.0	0.025	0.09058
0.73567	0.43104	180 156	120 104	0.56	0.38	-1.5	0.025	0.26433
0.46930	0.14923	180 156	120 104	0.56	0.38	-1.0	0.025	0.5307
0.21648	0.02834	180 156	120 104	0.56	0.38	-0.5	0.025	0.78352
0.06795	0.00279	180 156	120 104	0.56	0.38	0.0	0.025	0.93205

C) MARS Group Sequential Clinical Trial Design

MARS Preliminary Data. For patients that had a history of previous ablation (original MARS trial sample size calculations) the pilot data showed that among 169 patients we observed a response rate of $p_1=42\%$ for repeat PVAI and $p_2=76\%$ for 32 patients undergoing VOM-PV.

Power and sample size determination. Group sequential two proportions power analysis using simulation was performed using PASS V12 (Kaysville, UT). The following assumptions were made:

- Response rate in PV-VOM: $p_1=0.76$

- Response rate in PVAI: $p_2 = 0.42$
- Hypotheses: $H_0: p_1 = p_2$; $H_1: p_1 \neq p_2$
- Test Statistic: Z-Test (Unpooled)
- Zero Adjustment Method: None
- Alpha-Spending Function: O'Brien-Fleming Analog
- Beta-Spending Function: None
- Futility Boundary Type: None
- Number of Looks: 3
- Simulations: 100000

Table 9. Sample size requirements for a group sequential trial based on 100,000 iterations.

Value	Power			Alpha				Beta	

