	95% LCL	95% UCL	Target	Actual	95% LCL	95% UCL			
0.810	0.807	0.812	0.050	0.049	0.047	0.050	0.190		
----- Average Sample Size -----									
-- Given H_0 -- -- Given H_1 --									
N1	N2	Grp1	Grp2	Grp1	Grp2	Diff0	Diff1	P1 H1	P2
33	33	33	33	28	28	0.00	0.34	0.76	0.42

Results. Group sequential trials with sample sizes of 33 and 33 at the final look achieve 81% power to detect a difference of 0.34 between a treatment group proportion of 0.76 and a control group proportion of 0.42 at the 0.05 significance level (alpha) using a two-sided Z-Test (Unpooled).

Efficacy Monitoring. We propose to monitor efficacy at two interim time points and one final time period (i.e., three “looks”) when primary outcome data (12-15 month follow-up) are available for 1/3, 2/3 and 3/3 of the total sample size of MARS subjects. For the MARS trial, these values are provide in the following table in terms of *information time*:

Table 10. Efficacy monitoring schedule for MARS with cumulative sample size, significance boundaries and 95%CIs, and alpha- and beta-spending.

Accumulated primary outcomes for MARS												
Look	Information Percent	Accumulated Sample Size			Z-Value Boundary			P-Value Boundary				
		Group 1	Group 2	Total	Value	95% LCL	95% UCL	Value	95% LCL	95% UCL		
1	33.33	11	11	22								
2	66.67	22	22	44								
3	100.00	33	33	66								
Significance Boundaries with 95% Simulation Confidence Intervals for Scenario 1												
----- Z-Value Boundary -----			----- P-Value Boundary -----									
Look	Value	95% LCL	95% UCL	Value	95% LCL	95% UCL	Value	95% LCL	95% UCL	Value	95% LCL	95% UCL
1	+/- 5.014	5.014	6.675	0.000	0.000	0.000						
2	+/- 2.708	2.640	2.708	0.007	0.007	0.008						
3	+/- 2.055	2.055	2.080	0.040	0.037	0.040						
Alpha-Spending												

Look	----- Target -----		----- Actual -----		Proportion		Cum.		H1 Sims		H1 Sims	
	-- Signif.	Boundary--	Spending	Spending	Cum.	Alpha	Cum.	Alpha	Outside	Signif.	Outside	Signif.
Z-Value	Scale	P-Value	Scale	Function	Alpha	Spent	Alpha	Spent	Boundary	Signif.	Boundary	Signif.
1	+/- 5.014	0.000	0.000	0.000	0.000	0.000	0.000	0.000	0.017	0.017	0.422	0.422
2	+/- 2.708	0.007	0.012	0.012	0.010	0.010	0.011	0.011	0.404	0.404	0.810	0.810
3	+/- 2.055	0.040	0.038	0.050	0.038	0.038	0.049	0.049	0.388	0.388		

[figure not shown]

Figure S2. Efficacy boundaries at 33%, 66%, and 100% accrual of MARS primary outcomes.

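### MARS power, looks and boundaries are calculated for 33/33 (N=66), but the trial plans 37/32 (N=69) at 1.15:1; the 81% power survives, but the printed counts and boundaries do not match the trial

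*Combined protocol and SAP*

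**What the plan says.** - **Planned size.** The Protocol Synopsis gives "MARS: 37 (VOM-PV) + 32 (PVAI) = 69".
- **Allocation.** Section 5.5, Randomization: "Patients will be randomized in a 1.15:1 fashion". The stated reason is the 85% technical feasibility of the VOM procedure.
- **Design calculation.** Section 6.0 C, Results: "Group sequential trials with sample sizes of 33 and 33 at the final look achieve 81% power", for success rates of 0.76 (VOM-PV) and 0.42 (PVAI) and an unpooled two-sided Z test at 0.05. Table 9 uses 33 per arm. Table 10 lists looks at 11/11, 22/22 and 33/33 with boundaries 5.014, 2.708 and 2.055. Tables 11 and 12 and the MARS missing-data tables use the same equal arms.
- **Spending.** Section 6.0 C lists "Alpha-Spending Function: O'Brien-Fleming Analog".
- **Look timing.** The MARS efficacy-monitoring paragraph triggers looks at one third, two thirds and all of the total MARS sample, on "primary outcome data (12-15 month follow-up"). The VENUS paragraph uses 12 months.
- **Use of the boundaries.** Section 6.0, Statistical Analyses, Primary Outcome, takes the critical values of the primary test from these tables.
- **Fixed size and exclusions.** Section 6.0 C rules out any change of sample size. Section 6.0 A drops unclassifiable patients from the primary analysis.

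**The concern.** The MARS calculation has a different total (66 against 69), a different allocation (1:1 against 1.15:1) and different look counts from the trial described elsewhere in the same document. No text connects the two. VENUS, by contrast, uses its planned 180/156 in every design table.

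More than presentation is at stake, because the printed boundaries are the thresholds of the confirmatory test. In a trial this small the Z statistic takes few values, and boundaries found by simulation depend on the exact counts. If they are applied at other counts without a rule, the type I error is no longer the one the plan reports. The interim crossing probabilities and conditional-power tables that inform continuation decisions are also for the wrong counts.

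**Working it through.** **Inputs.** Rates 0.76 and 0.42, unpooled Z, two-sided 0.05, three looks (Section 6.0 C); boundaries 5.014, 2.708, 2.055 (Table 10); 37/32 (Synopsis); 1.15:1 (Section 5.5). No loss rate is stated for MARS, so 5% and 10% in both arms are assumptions.

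**1. Can the two sets of counts be reconciled?**
- 69 × 1.15/2.15 = 36.9, so 37/32 is the deliberate 1.15:1 split of 69.
- 66 × 1.15/2.15 = 35.3, so 66 at that ratio is 35/31, not 33/33.
- Attrition cannot turn 32 planned PVAI patients into 33.
- Cannulation success gives 0.85 × 37 = 31.5 in the VOM-PV arm, not 33, and does not touch the PVAI arm.

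**2. Reproducing the stated power.** At each look Z = (p̂1 − p̂2) / √[p̂1(1 − p̂1)/n1 + p̂2(1 − p̂2)/n2]. All binomial outcomes were enumerated exactly, rejecting when |Z| exceeds the boundary. At 11/11, 22/22, 33/33 the cumulative power is 0.017, 0.397, 0.811 (printed 0.017, 0.422, 0.810). Type I error is 0.048 to 0.049 at null rates 0.42, 0.59 and 0.76 (printed 0.049). The 81% reproduces. The printed second-look figure lies between 0.397 and 0.426, the latter if reaching the boundary counts as crossing it.

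**3. Are the boundaries tied to those counts?** Each is an attainable Z value of the equal-arm design:
- 5.014 is 9/11 against 1/11.
- 2.708 is 18/22 against 10/22.
- 2.055 is 23/33 against 15/33: (0.6970 − 0.4545)/√(0.2112/33 + 0.2479/33) = 0.2424/0.1180 = 2.055.

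**4. The printed boundaries at other counts.**

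| Final counts (interim looks) | Power | Type I error at null rate 0.30 / 0.42 / 0.59 / 0.76 |
|---|---|---|
| 33/33 (11/11, 22/22) | 0.811 | 0.050 / 0.048 / 0.049 / 0.049 |
| 37/32 (12/11, 25/21) | 0.816 | 0.048 / 0.049 / 0.049 / 0.052 |
| 37/32 (12/11, 24/22) | 0.815 | 0.048 / 0.049 / 0.049 / 0.053 |
| 35/31, i.e. 66 at 1.15:1 (12/10, 23/21) | 0.801 | 0.048 / 0.048 / 0.048 / 0.049 |
| 35/30, assumed 5% loss (12/10, 23/20) | 0.832 | 0.060 / 0.056 / 0.057 / 0.056 |
| 33/29, assumed 10% loss (11/10, 22/19) | 0.776 | 0.051 / 0.053 / 0.052 / 0.052 |

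The information for the difference at 37/32 is 1/(0.1824/37 + 0.2436/32) = 79.7, against 1/(0.1824/33 + 0.2436/33) = 77.5 at 33/33, a ratio of 1.03. That is why power barely moves. The higher power at 35/30 is no gain; it is the counterpart of the raised type I error there.

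**5. Interim probabilities.** At 37/32 the cumulative chance of crossing under the design rates is 0.029 at look 1 (printed 0.017) and 0.446 to 0.467 at look 2 (printed 0.422).

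**6. Follow-up wording.** The 12-month visit (day 360) has a window of 60 days and the monitor runs up to 28 days: 360 + 60 + 28 = 448 days, or 448/30.44 = 14.7 months.

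**The case against.** The best defence is that nothing of substance changes. The 81% is correct for the design it describes, so there is no arithmetic error. At 37/32 the printed boundaries hold the error rate about as well as at 33/33, and power is marginally higher. The rates, test, alpha, number of looks and information fractions are all unaffected. The plan also names a spending function, which is the usual basis for adapting boundaries to other look sizes. All of this stands, and it limits the point. It does not remove the mismatch in total, split and look counts, and the plan never says that the boundaries will be recomputed.

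Three stronger readings are tempting and should not be drawn:
- **That the final look cannot take place.** MARS looks are triggered by fractions of the total sample, and 37/32 meets that text. The wording that requires a minimum number in each arm is written for VENUS only. What cannot be reached, on the planned numbers, is the 33/33 row. The randomisation method is not described, so realised counts may also differ by chance from 37/32.
- **That MARS is underpowered by the mismatch.** It is not, when all patients are classified.
- **That the 12 to 15 month outcome time is an error.** Section 6.0 A attributes follow-up of up to 15 months to previous protocol versions, and for VENUS, so the phrase may be left over. But the current visit window plus monitor can run to about 14.7 months, so the phrase is compatible with the schedule and blocks no look.

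**Conclusion.** The inconsistency holds and should be corrected, but it is one of specification and not a loss of power. The stated sample size, arm split, look counts and simulated critical values for MARS are not those of the planned trial. With every patient classified and the printed boundaries, power at 37/32 is about 0.815 and type I error 0.048 to 0.053.

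The practical exposure is the missing rule for actual counts. It shows as a type I error of about 0.056 to 0.060 at 35/30 (null rates 0.30 to 0.76), and as power of about 0.78 at 33/29. These two results rest on assumed losses of 5% and 10%, equal in both arms, and on look counts close to the planned fractions. The plan gives no loss rate against which to judge how likely they are.

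**What to change.** - Re-run the MARS design at 37/32, with looks at about 12/11, 25/21 and 37/32. Replace Tables 9 to 12 and the MARS missing-data tables.
- State N=69, and power of about 0.81 to 0.82 if all patients are classified.
- State that the boundary at each look will be recomputed from the named O'Brien-Fleming-type spending function at the classified counts actually available. Without this sentence, a new set of fixed counts would repeat the problem.
- As a wording alignment only, describe the MARS looks by the 12-month outcome used for VENUS.

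The cost is a re-run of the design and replacement tables. Enrolment and allocation do not change.
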